3.4.3 Packaging and Labeling

For research only	Protocol ID: 2018-120
Lipoic Acid Capsules for Clinical Trial Use	
Drug ID: _____	Name Abbreviation: _____
Dispensing Date: _____	
Dosage and Administration: Take 2 capsules at a time, three times daily.	
Packaging: Each bottle contains xx capsules.	
Storage: Keep the container tightly closed. Expiration Date: XXXX	
All unused medication, along with its original packaging, must be returned to the investigator.	
Keep out of reach of children	

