3.4 Investigational Drugs

3.4.1 Investigational Medicinal Products:

Investigational Drug: Lipoic Acid Capsules

Placebo: Contains starch as the inert ingredient, with an identical appearance to the investigational drug

3.4.2 Dosage Form, Dose, Route of Administration, Administration Method, Frequency of Administration, and Treatment Duration

Dosage Form: 100mg capsules

Dose: 600mg per day

Route of Administration: Oral

Frequency of Administration: 200mg per dose, administered three times daily

Treatment Duration: 24 months

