3.4.4 Drug Interactions

Lipoic acid acts as a metal chelator, hence particular caution should be exercised to avoid taking it concurrently with medications containing metal components (such as iron and magnesium preparations).

Additionally, it should not be taken simultaneously with milk due to its calcium content. If lipoic acid is administered half an hour before breakfast, iron and magnesium preparations can be taken during lunch or dinner.

Lipoic acid may potentiate the hypoglycemic effects of insulin and oral antidiabetic drugs. Therefore, it is recommended to monitor blood glucose levels regularly, especially when initiating treatment with this product. In some patients, to prevent the occurrence of hypoglycemic symptoms, it may even be necessary to reduce the dosage of insulin and oral antidiabetic medications.

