3.5 Research Procedures

3.5.1 Screening and Enrollment Period

At the hospital's heart failure outpatient clinic and inpatient ward, consecutive patient screening was initiated based on inclusion and exclusion criteria. Detailed information about the study objectives, significance, and procedures was provided to patients. Their consent was obtained, and informed consent forms were signed.

Eligible patients were randomized in a 1:1 ratio to either the lipoic acid capsule group or the control group. Patients continued their current optimized medications and additionally received the study drug.

ALA Group:

Standard treatment for post-myocardial infarction heart failure + lipoic acid capsules (1 capsule/dose, 3 times/day for the first week, escalated to 2 capsules/dose, 3 times/day thereafter, swallowed with warm water).

Placebo Group:

Standard treatment for post-myocardial infarction heart failure + placebo (1 capsule/dose, 3 times/day for the first week, escalated to 2 capsules/dose, 3 times/day thereafter, swallowed with warm water).

Concomitant Standard Therapy (Medications and Devices):

Patients should adhere to current treatment guidelines[29], with therapies tailored by clinicians based on individual conditions. Risk factors such as blood glucose, blood pressure, and lipids should be controlled. Patients should receive dietary guidance for cardiac health (e.g., low-salt diet) and lifestyle modifications, including weight monitoring, physical exercise, smoking cessation, and alcohol restriction. Device-based therapies, including but not limited to stent implantation, may be administered according to current guidelines and patient conditions.

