3.5.2 Follow-up Period

Patients underwent baseline visits on Day 0 post-randomization, followed by visits at Months 6, 12, and 24, totaling 4 on-site visits for efficacy, compliance, and safety assessments until study completion. The follow-up period lasted 24 months.

Visit 1 (Screening and Enrollment Period)

Inclusion and exclusion criteria

Informed consent signing

Past medical history and comorbidities

Comprehensive physical examination

Detailed documentation of medical history, comorbidities, treatment, concomitant medications, blood pressure, heart rate, weight measurement.

Cardiac function assessment (6-minute walk test: 6MWD)

Electrocardiogram (ECG)

Echocardiography

Laboratory tests: blood/urine/biochemical parameters, brain natriuretic peptide (BNP), coagulation function

Distribution of study medication

Instructions for the next follow-up visit date and brief physical examination

Visit 2 (Month 6 post-randomization), Visit 3 (Month 12 post-randomization), Visit 4 (Month 24 post-randomization)

Heart failure symptoms and signs

Comprehensive physical examination

Blood pressure, heart rate, weight measurement

Documentation of primary and secondary endpoint events

Adverse event recording

Cardiac function assessment (6MWD)

ECG

Echocardiography

Laboratory tests (blood/urine/biochemical parameters, BNP), coagulation function

Distribution/collection of study medication

Instructions for the next follow-up visit date or study termination

During months without on-site visits, researchers should contact patients via telephone to inquire about adverse events, endpoint events, and changes in concomitant medications, completing corresponding records.

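### The bottle label omits the lower first-week dose set in section 3.5.1, so a patient who follows it starts at 600 instead of 300 mg/day

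*Protocol*

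**What the plan says.** Three parts of the protocol state the dose.

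- Section 3.4.2 gives the capsule strength ("Dosage Form: 100mg capsules"), the daily amount ("Dose: 600mg per day") and the schedule ("200mg per dose, administered three times daily"). It mentions no starting week.
- Section 3.4.3 shows one label. Its dosing line reads "Take 2 capsules at a time, three times daily". Drug ID, dispensing date, bottle count and expiry are left open, but the dosing line is complete.
- Section 3.5.1 sets out the regimen in the same words for the active and placebo arms: "1 capsule/dose, 3 times/day for the first week, escalated to 2 capsules/dose, 3 times/day thereafter".

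Two other sections bear on the consequence. Section 3.4.4 notes that lipoic acid may strengthen the effect of insulin and oral antidiabetic drugs, and says "it is recommended to monitor blood glucose levels regularly, especially when initiating treatment with this product". Section 3.5.2 has study medication handed out at Visit 1, "followed by visits at Months 6, 12, and 24", with telephone contact in months that have no on-site visit.

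**The concern.** The label and section 3.5.1 cannot both be followed in week 1. A patient who does what the bottle says skips the titration step and takes twice the prescribed first-week dose. No visit or call is tied to day 7, when the dose should change, so on the protocol's text the label is the dosing instruction the patient then has at hand.

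What is at stake is early tolerability and consistency of the prescribed regimen. Diabetes is not an exclusion criterion in section 3.2 and is a planned subgroup in section 5.2.3, so some participants are likely to be on glucose-lowering drugs. A patient who obeys the label would also depart from section 3.5.1 through no fault of their own, in a trial that assesses compliance at its visits and lists poor compliance among its withdrawal criteria (section 3.2).

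**Working it through.** **Inputs.** Capsule strength 100 mg (section 3.4.2). Label: 2 capsules, 3 times daily (section 3.4.3). Titration: 1 capsule, 3 times daily for 7 days, then 2 capsules, 3 times daily (section 3.5.1). Treatment lasts 24 months (section 3.4.2), taken here as 730 days; that conversion is an assumption.

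**Formula.** Daily dose = capsules per dose × doses per day × mg per capsule.

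**The plan's own figure.** 2 × 3 × 100 = 600 mg/day. This reproduces section 3.4.2 and matches the label.

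**Week 1, active arm**

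| | Label (3.4.3) | Titration (3.5.1) |
|---|---|---|
| Daily dose | 2 × 3 × 100 = 600 mg | 1 × 3 × 100 = 300 mg |
| Capsules over 7 days | 6 × 7 = 42 | 3 × 7 = 21 |
| Total over 7 days | 600 × 7 = 4,200 mg | 300 × 7 = 2,100 mg |

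The ratio is 600 / 300 = 2.

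**Week 2 onward.** Both give 2 × 3 × 100 = 600 mg/day, so there is no conflict.

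**Whole treatment period**

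- Label: 600 × 730 = 438,000 mg.
- Section 3.5.1: 2,100 + 600 × (730 − 7) = 2,100 + 433,800 = 435,900 mg.
- Difference: 2,100 mg, and 2,100 / 438,000 = 0.48%.

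**Placebo arm.** Only the number of inert capsules would differ (42 against 21 in week 1). The protocol shows no placebo label.

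**The case against.** The strongest reply is that section 3.5.1 is the operative procedure and is unambiguous. On that reading section 3.4.2 states a target dose, and section 3.4.3 is only a specimen with several blanks. It might be the maintenance label, with staff explaining the first week when they hand out the medication. Patient-facing text outside the protocol could also carry the step.

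The target-dose reading of section 3.4.2 is reasonable, which makes that section weak evidence of a conflict. It does not help the label, which is an instruction to the patient with a completed dosing line and no first-week exception. Spoken advice is plausible, but the protocol does not call for it, and it would have to override the printed text. No separate starter label or bottle is described.

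The objection to the safety argument has more force. The protocol gives no reason for the titration. The glucose advice in section 3.4.4 applies at either starting dose, and nothing in the document shows that starting at 600 mg/day carries more risk of hypoglycaemia than starting at 300 mg/day. The background section puts adverse reactions below 1 in 10,000. The link between the skipped step and hypoglycaemia is therefore an inference. The worst case is that a patient reaches the intended dose seven days early.

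**Conclusion.** The contradiction is real and confined to week 1: the label gives 600 mg/day where section 3.5.1 prescribes 300 mg/day. It should be corrected because it is a patient instruction that, if followed, departs from the prescribed regimen at the start of treatment.

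The point is minor. The difference is 2,100 mg, or 0.48% of planned 24-month exposure. The regimen is the same in both arms, so the inconsistency does not threaten the blind, and any effect on the primary endpoint is negligible. The dose figures rest only on the stated capsule strength and schedules. The percentage also assumes 730 days. The conclusion that patients could be misdirected assumes that the label shown is the one on the first bottle, and the protocol describes no other.

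**What to change.** Change the dosing line on the label, in both arms, to 1 capsule three times daily for the first 7 days and 2 capsules three times daily from then on. In section 3.4.2, add that 600 mg/day applies after a first week at 300 mg/day.

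If the investigators do not intend a titration, delete the week-1 step from section 3.5.1 in both arms and leave the label as it is.

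Either option costs a line or two of text and leaves visits, sample size and analysis unchanged. A separate week-1 bottle would also resolve the conflict, but it adds blinded packaging and drug accountability at four centres, so the label change is preferable.

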3.4.4 Drug Interactions

Lipoic acid acts as a metal chelator, hence particular caution should be exercised to avoid taking it concurrently with medications containing metal components (such as iron and magnesium preparations).

Additionally, it should not be taken simultaneously with milk due to its calcium content. If lipoic acid is administered half an hour before breakfast, iron and magnesium preparations can be taken during lunch or dinner.

Lipoic acid may potentiate the hypoglycemic effects of insulin and oral antidiabetic drugs. Therefore, it is recommended to monitor blood glucose levels regularly, especially when initiating treatment with this product. In some patients, to prevent the occurrence of hypoglycemic symptoms, it may even be necessary to reduce the dosage of insulin and oral antidiabetic medications.

3.5 Research Procedures

3.5.1 Screening and Enrollment Period

At the hospital's heart failure outpatient clinic and inpatient ward, consecutive patient screening was initiated based on inclusion and exclusion criteria. Detailed information about the study objectives, significance, and procedures was provided to patients. Their consent was obtained, and informed consent forms were signed.

Eligible patients were randomized in a 1:1 ratio to either the lipoic acid capsule group or the control group. Patients continued their current optimized medications and additionally received the study drug.

ALA Group:

Standard treatment for post-myocardial infarction heart failure + lipoic acid capsules (1 capsule/dose, 3 times/day for the first week, escalated to 2 capsules/dose, 3 times/day thereafter, swallowed with warm water).

Placebo Group:

Standard treatment for post-myocardial infarction heart failure + placebo (1 capsule/dose, 3 times/day for the first week, escalated to 2 capsules/dose, 3 times/day thereafter, swallowed with warm water).

Concomitant Standard Therapy (Medications and Devices):

Patients should adhere to current treatment guidelines[29], with therapies tailored by clinicians based on individual conditions. Risk factors such as blood glucose, blood pressure, and lipids should be controlled. Patients should receive dietary guidance for cardiac health (e.g., low-salt diet) and lifestyle modifications, including weight monitoring, physical exercise, smoking cessation, and alcohol restriction. Device-based therapies, including but not limited to stent implantation, may be administered according to current guidelines and patient conditions.

3.5.2 Follow-up Period

Patients underwent baseline visits on Day 0 post-randomization, followed by visits at Months 6, 12, and 24, totaling 4 on-site visits for efficacy, compliance, and safety assessments until study completion. The follow-up period lasted 24 months.

Visit 1 (Screening and Enrollment Period)

Inclusion and exclusion criteria

Informed consent signing

Past medical history and comorbidities

Comprehensive physical examination

Detailed documentation of medical history, comorbidities, treatment, concomitant medications, blood pressure, heart rate, weight measurement.

Cardiac function assessment (6-minute walk test: 6MWD)

Electrocardiogram (ECG)

Echocardiography

Laboratory tests: blood/urine/biochemical parameters, brain natriuretic peptide (BNP), coagulation function

Distribution of study medication

Instructions for the next follow-up visit date and brief physical examination

Visit 2 (Month 6 post-randomization), Visit 3 (Month 12 post-randomization), Visit 4 (Month 24 post-randomization)

Heart failure symptoms and signs

Comprehensive physical examination

Blood pressure, heart rate, weight measurement

Documentation of primary and secondary endpoint events

Adverse event recording

Cardiac function assessment (6MWD)

ECG

Echocardiography

Laboratory tests (blood/urine/biochemical parameters, BNP), coagulation function

Distribution/collection of study medication

Instructions for the next follow-up visit date or study termination

During months without on-site visits, researchers should contact patients via telephone to inquire about adverse events, endpoint events, and changes in concomitant medications, completing corresponding records.

3.6 Study Endpoint

3.6.1 Primary Endpoint:

A composite endpoint of all-cause death and rehospitalization due to heart failure during the 24-month follow-up period.

3.6.2 Secondary Endpoints:

The second endpoints included all-cause death and rehospitalization due to heart failure, non-fatal MI or non-fatal stroke during the 24-month follow-up period. The changes of LVEF and 6MWD were also assessed from baseline to 24 months.

3.6.3 Endpoint Definitions

All-cause death is defined as death due to any cause.

Rehospitalization due to heart failure is defined as nonelective repeat hospitalization in all patients alive at discharge for heart failure.

MI is defined based on the Fourth Universal Definition of Myocardial Infarction, which encompassed clinical evidence of acute myocardial ischemia and with detection of a rise and/or fall of cardiac troponin (cTn) values, with at least 1 value above the 99th percentile upper reference limit (URL) and at least 1 of the following: symptoms of myocardial ischemia; new ischemic electrocardiogram changes; development of pathological Q waves; imaging evidence of new loss of viable myocardium or new regional wall motion abnormality in a pattern consistent with an ischemic etiology, identification of a coronary thrombus by angiography

Stroke is defined on the basis of the presence of acute infarction as demonstrated by imaging or based on the persistence of symptoms.

四、Adverse Event

4.1 Definitions

Adverse Event (AE): Any untoward medical occurrence in a patient or clinical trial subject following the administration of a pharmaceutical product, which does not necessarily have a causal relationship with the treatment.

Serious Adverse Event (SAE): An event occurring during the clinical trial that results in hospitalization, prolongation of hospitalization, disability, impairment of work ability, life-threatening condition, death, congenital anomaly, or other significant medical events.

4.2 Severity

Mild: The event is tolerable to the subject, does not affect treatment, requires no special intervention, and has no impact on the subject's recovery.

Moderate: The event is intolerable to the subject, requires special intervention, and has a direct impact on the subject's recovery.

Severe: The event is life-threatening, leads to death or disability, and requires immediate emergency intervention.

4.3 Documentation and Reporting of Adverse Events

Clinical adverse events may occur during the subject's treatment. Once an adverse event (including significant adverse events) occurs, the following details should be recorded in detail on the Case Report Form (CRF): time of occurrence, clinical manifestations, management, duration, outcome, and relationship to the study drug. For subjects with abnormal laboratory test results, follow-up should be conducted until the results return to normal, to the pre-treatment level, or until it is confirmed that the abnormalities are unrelated to the study drug. In the case of a serious adverse event, a Serious Adverse Event Form should be completed and reported to the sponsor, ethics committee, CFDA Safety Monitoring Department, and health administrative department within 24 hours.

4.4 Risk Prevention and Management

The investigator should assess the clinical significance of abnormal laboratory results and provide possible explanations. Laboratory abnormalities resulting from previously reported adverse events should

also be recorded as adverse events in the Adverse Event Form. Laboratory abnormalities with clinical significance that meet one or more of the following criteria should be recorded as independent diagnoses in the Adverse Event section of the CRF (excluding abnormalities resulting from previously reported adverse events):1.Accompanied by clinical symptoms ; 2.Leading to changes in clinical medication ; 3.Requiring modification of concomitant therapy.

For unexplained abnormal laboratory values, repeat testing should be performed, and follow-up should continue until the value returns to the normal reference range or baseline, and/or a reasonable explanation is found. If a clear explanation is identified, it should be documented on the CRF.

During the clinical trial, investigators should closely monitor the occurrence of serious adverse events. Upon the occurrence of a serious adverse event, necessary measures should be taken first to ensure the safety of the subject, followed by reporting to the sponsor, contract research organization (CRO), and the ethics committee of the center within 24 hours.

All safety follow-up visits will be conducted 15 days after the end of the study visit. For subjects who withdraw prematurely, safety follow-up will also be conducted 15 days after the end of the study visit, unless the investigator deems it necessary for the subject to return to the hospital for follow-up measurements due to persistent adverse events at the end of treatment or clinically significant abnormalities in laboratory tests or vital signs. Safety follow-up may be conducted via telephone.

五、 Statistic Method

5.1 Sample Size Calculation

This pilot and feasibility study was designed to evaluate the efficacy and safety of ALA in IHF patients and get the reference data on outcomes related to clinical events for the future RCT with large sample size. As a feasibility trial, 300 patients were expected to be enrolled during the study period. Assumptions for sample size calculation included the following: the event rate for primary outcomes was 35% at 24 months in the control group[30]; the HR for the ALA group was estimated to be 0.60 and a withdrawal rate of 5% at 24 months in both groups. A total of 300 (150 per group) subjects followed up for a fixed period of 24 months provides 80% power to reject the null hypothesis at the two-sided 0.1 significance level.

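### Section 5.1 claims 80% power at two-sided 0.1, but its own inputs give about 75% to 77%

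*Protocol*

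**What the plan says.** Protocol Section 5.1 gives a full set of planning assumptions. For the control arm, "the event rate for primary outcomes was 35% at 24 months in the control group". For the effect, "the HR for the ALA group was estimated to be 0.60". For losses, "a withdrawal rate of 5% at 24 months in both groups". It then concludes that 150 subjects per group "subjects followed up for a fixed period of 24 months provides 80% power to reject the null hypothesis", with a two-sided significance level of 0.1. It names no formula or software, no event rate for the lipoic acid arm and no expected number of events.

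The same section calls the trial a pilot and feasibility study, and gives 300 as the enrolment expected of a feasibility trial before it turns to the power assumptions. Section 3.5.1 confirms the allocation: "Eligible patients were randomized in a 1:1 ratio". Section 5.2.3 fixes the analysis as time to first event with a Cox hazard ratio, and sets the two-sided type I error at 0.05.

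**The concern.** The effect is stated as a hazard ratio and the analysis is time to event, so power depends mainly on the number of events. The stated rates produce fewer events than 80% power requires at a hazard ratio of 0.60, even at the lenient 0.1 level that the section itself uses.

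Two things are at stake. A null result would be read against an overstated chance of detecting the assumed effect: the miss probability at 0.1 is about 24%, not 20%. And because the inputs and the power do not fit together, a reader cannot tell which of them was really assumed.

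This is separate from the conflict between 0.1 in Section 5.1 and 0.05 in Section 5.2.3. Settling on 0.1 throughout would leave the 80% still wrong.

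**Working it through.** **Inputs.** From Section 5.1: control event rate 0.35 at 24 months, hazard ratio 0.60, withdrawal 5% in each arm, 150 per arm, fixed 24 months of follow-up, two-sided alpha 0.1, so z = 1.645. The figure to reproduce is 80%.

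**Event rate on lipoic acid.** Under proportional hazards, 1 − (1 − 0.35)^0.60 = 0.228.

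**Expected events.** Section 5.1 does not say how withdrawal enters, so three versions:

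- No withdrawal: 150 × (0.35 + 0.228) = 86.7.
- Exponential withdrawal reaching 5% at 24 months. Yearly hazards are −ln(0.65)/2 = 0.2154 (control), 0.60 × 0.2154 = 0.1292 (lipoic acid) and w = −ln(0.95)/2 = 0.0256 (withdrawal). The event probability is λ/(λ + w) × [1 − exp(−2(λ + w))], which is 0.342 and 0.222. Events: 84.6.
- 5% of patients removed, 142.5 per arm: 142.5 × (0.35 + 0.228) = 82.3.

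**Power at two-sided 0.1.** Schoenfeld: Φ(√d/2 × |ln 0.60| − 1.645). Freedman: Φ(√d × (1 − 0.60)/(1 + 0.60) − 1.645).

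| Withdrawal | Events | Schoenfeld | Freedman |
|---|---|---|---|
| None | 86.7 | 76.8% | 75.3% |
| Exponential 5% | 84.6 | 75.9% | 74.4% |
| 5% removed | 82.3 | 74.9% | 73.4% |

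For example, with 84.6 events: 9.198/2 × 0.5108 − 1.645 = 0.704, and Φ(0.704) = 75.9%.

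**Cross-checks.** A log-rank simulation of 20,000 trials gives 75.7% with exponential withdrawal and 76.6% without. An uncorrected two-proportion test of 35% against 22.8% gives 75.7% with 150 per arm and 73.8% with 142.5. A continuity correction lowers the 150-per-arm figure to 71.5%. The 80% is not reproduced, even when withdrawal is ignored.

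**Events and patients for 80%.**

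- Schoenfeld: 4 × (1.645 + 0.842)² / (ln 0.60)² = 94.8, so 95 events.
- Freedman: (1.60/0.40)² × (1.645 + 0.842)² = 98.9, so 99 events.
- With an average event probability of (0.35 + 0.228)/2 = 0.289 and no withdrawal: 95/0.289 ≈ 329 and 99/0.289 ≈ 343 patients.
- With exponential withdrawal (average probability 0.282): about 337 and 351.
- Dividing the no-withdrawal figures by 0.95: about 346 and 361.

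Against 300 planned, the shortfall is therefore 29 to 61 patients, depending on formula and withdrawal handling.

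**What would return about 80%.** Each route changes something that the text states:

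- 35% read as the rate over both arms: 300 × 0.95 × 0.35 = 99.75 events, power 80.3% (Freedman) or 81.8% (Schoenfeld). In reverse, 99/0.35/0.95 = 298 patients.
- 0.60 read as a risk ratio: 0.35 × 0.60 = 0.21. A continuity-corrected two-proportion test needs 141 per arm, and 141/0.95 = 149; power with 142.5 per arm is 80.7%. The hazard ratio behind 35% against 21% would be ln(0.79)/ln(0.65) = 0.55.
- With exponential withdrawal and the other inputs fixed, a control rate near 39% (80.0%) or a hazard ratio near 0.58 (80.1%).

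A one-sided test at 0.10 overshoots, at 84% to 86%.

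**At two-sided 0.05**, Schoenfeld gives 66.2%, 65.2% and 64.0% for the three event counts.

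**The case against.** The best case for leaving the text alone is that the gap is small. About 4 points is within the uncertainty of planning assumptions for a pilot: a hazard ratio of 0.58, or a control rate of 39%, would close it. Section 3.1 calls the trial exploratory, and a later trial would be planned from observed event rates and an estimated effect rather than from this power figure. The alpha conflict moves power further, from about 76% to about 65%. All of this stands, and it limits the weight of the point. It does not make 80% a correct consequence of the stated inputs.

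Two stronger readings are tempting. A reader might infer that the sponsor mistook a risk ratio for a hazard ratio. The document does not support that: treating 35% as the rate over both arms also leads to about 300 patients and 80%, and keeps the hazard ratio and the time-to-event test. No method is named, so the origin of 300 is unknown. A reader might also infer that 300 has no valid basis once the power claim fails. Section 5.1 gives feasibility as a reason as well, so the power statement is not its sole support.

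**Conclusion.** The stated 80% is wrong as written. With Section 5.1's own inputs at two-sided 0.1, power is about 75% to 77% by Schoenfeld's formula or 73% to 75% by Freedman's, from about 82 to 87 expected events against the 95 to 99 needed. The conclusion assumes proportional hazards and 1:1 allocation. The exponential-withdrawal figures and the simulation also assume constant event hazards. The conclusion does not depend on how withdrawal is handled, because the shortfall remains with none. The error is modest, and it does not show that the trial must be enlarged.

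**What to change.** Keep 300 patients and correct Section 5.1. Name the method and how withdrawal enters it, give the lipoic acid event rate as 1 − 0.65^0.60 = 22.8%, and give the expected number of events (about 85). Then restate the power: about 76% for a hazard ratio of 0.60 at two-sided 0.1, or equivalently 80% for a hazard ratio of about 0.58.

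Two conditions apply. If an input was misdescribed, for instance if 35% was meant for both arms or 0.60 as a risk ratio, correct that input instead. And compute the figure at whichever alpha is kept once Sections 5.1 and 5.2.3 have been reconciled; at 0.05 it is about 65%.

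The cost is a sentence or two of text and a less favourable power figure. No further patients are needed.

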3.1 Design

This is a multicenter, double-blind, randomized, placebo-controlled, parallel-group, exploratory trial.

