5.2.3 Statistical Methods

All statistical analyses were performed with R version 4.0.2. Normally distributed continuous variables were reported as the mean \pm SD, and non-normally distributed continuous variables were expressed as the median and interquartile range. Categorical data were expressed as absolute values and percentages and analyzed using the chi-square or Fisher's exact test. The Student's t-test or Wilcoxon rank-sum test was performed to determine differences between groups. Survival analyses were based on the time to the first event. The cumulative incidence of the time-to-event end points is expressed as Kaplan-Meier curves over 24 months after randomization. Cox proportional hazard models were used to estimate HR and 2-sided 95% CI. A linear mixed-effects model was used to analyze the differences in changes of LVEF and 6MWD between the ALA group and the placebo group, with study centers included as random effects. Subgroup analysis was performed for age (whether \leq 65 years old), sex, smoking status, past medical history (hypertension, diabetes mellitus, atrial fibrillation), NYHA functional class, NT-proBNP levels, LVEF (whether \leq 30%), and whether the patient received triple therapy.

The analysis of safety and efficacy was performed in full analysis set (FAS) adhering to the intention-to-treat principle. The type I error rate (2-sided α) was set at 0.05.

六、Ethics

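### The 80% power is quoted at two-sided 0.1, but the analysis is set at two-sided 0.05, where the stated inputs give about 65%

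*Protocol*

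**What the plan says.** Protocol section 5.1 gives these inputs: "the event rate for primary outcomes was 35% at 24 months in the control group"; "the HR for the ALA group was estimated to be 0.60 and a withdrawal rate of 5% at 24 months in both groups"; 150 patients per group; and a fixed 24 months of follow-up. It concludes that the sample "provides 80% power to reject the null hypothesis at the two-sided 0.1 significance level".

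Protocol section 5.2.3 bases the survival analyses on time to first event and says "Cox proportional hazard models were used to estimate HR and 2-sided 95% CI". Directly after the sentence on the safety and efficacy analysis set it says "The type I error rate (2-sided α) was set at 0.05".

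On the trial's purpose, section 3.1 says "This is a multicenter, double-blind, randomized, placebo-controlled, parallel-group, exploratory trial" and section 5.1 says "As a feasibility trial, 300 patients were expected to be enrolled during the study period". Section 5.1 also names two aims: to evaluate efficacy and safety, and to supply reference data for a larger randomised trial. No section says that the primary endpoint is tested at 0.1, or that 0.05 applies only to other analyses.

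**The concern.** The protocol sizes the primary comparison at one significance level and tests it at another. Two things follow.

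- **The decision rule is ambiguous.** A primary p-value between 0.05 and 0.10 rejects the null hypothesis under section 5.1 and does not under section 5.2.3. If the level is chosen after unblinding, the choice is open to challenge.
- **The power figure does not describe the planned test.** A reader who takes 80% at face value will think that a true hazard ratio of 0.60 would be missed one time in five. At 0.05 the risk is larger. This matters because the result is meant to inform a larger trial, and a non-significant finding would be weighed against the wrong power.

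**Working it through.** **Inputs (section 5.1).** Control 24-month event rate 0.35; hazard ratio 0.60; withdrawal 5% in each arm; 150 per arm; two-sided alpha 0.10. **From section 5.2.3:** two-sided alpha 0.05.

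**Expected events.** Under proportional hazards the lipoic acid event rate is 1 − (1 − 0.35)^0.6 = 0.228.
- No withdrawal: 150 × (0.35 + 0.2278) = 86.7 events.
- 5% of patients lost entirely: 142.5 × 0.5778 = 82.3 events.
- Exponential withdrawal reaching 5% at 24 months: 84.6 events.

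**Formulas**, with d the number of events and z the two-sided critical value (1.645 at 0.10, 1.960 at 0.05):
- Schoenfeld: power = Φ(|ln 0.60| × √d / 2 − z)
- Freedman: power = Φ(√d × (1 − 0.60)/(1 + 0.60) − z) = Φ(0.25 × √d − z)

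For example, with 84.6 events Schoenfeld gives Φ(2.349 − 1.645) = 0.760 at 0.10 and Φ(2.349 − 1.960) = 0.652 at 0.05.

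| Method | Power at 0.10 | Power at 0.05 |
|---|---|---|
| Schoenfeld, 86.7 events | 76.8% | 66.2% |
| Schoenfeld, 84.6 events | 76.0% | 65.2% |
| Schoenfeld, 82.3 events | 74.9% | 64.0% |
| Freedman, 86.7 events | 75.3% | 64.3% |
| Freedman, 82.3 events | 73.4% | 62.1% |
| Simulated log-rank test, exponential withdrawal, 20,000 runs | 75.7% | 64.7% |

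**The plan's own figure.** The stated 80% at 0.10 is not reproduced; the inputs give 73% to 77%. For 80% power at 0.10, Schoenfeld needs 94.8 events and Freedman 98.9, which is about 345 and 360 patients after 5% loss.

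**Size of each effect.** Taking 80% at 0.10 at face value, the change of level alone gives Φ(1.645 + 0.842 − 1.960) = 70.1%. On the stated inputs the change of level costs about 11 points (76% to 65%). The other 4 points or so come from the 80% not reproducing at 0.10.

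**Events needed at 0.05.** For 80% power Schoenfeld needs 120.3 events and Freedman 125.6 (about 438 and 458 patients after 5% loss). The trial expects about 85.

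**Detectable effect with 300 patients (Schoenfeld, events recalculated at each hazard ratio).** 80% power corresponds to a hazard ratio of 0.53 to 0.54 at 0.05, and 0.58 at 0.10.

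**Other readings of the inputs.** Section 5.1 names no formula, so these are guesses at how 80% arose:
- 35% applied to both arms: 0.35 × 285 = 99.75 events. Freedman gives 80.3% at 0.10 and 70.4% at 0.05. This ignores the assumed benefit in the treated arm.
- 0.60 read as a risk ratio (35% against 21%), two proportions with continuity correction, 142.5 per arm: 80.7% at 0.10 and 70.8% at 0.05.
- The same risk-ratio reading with no correction and no loss: 77% to 78% at 0.05, depending on whether the variance is pooled.

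None of these reaches 80% at 0.05.

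**The case against.** The strongest reply is that this is a pilot. Its main product is a hazard ratio with an interval, to be used in planning a larger trial, and the power statement changes neither. Sizing a pilot at a relaxed level is legitimate, and section 5.1 openly attaches its 80% to the 0.1 level, so a careful reader can see the condition. A 95% interval does not by itself contradict a test at 0.1. Finally, setting 80% against 65% blends two defects, because the change of level alone accounts for a fall to only about 70%.

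Much of this stands. The design, the sample size, the data collected and the hazard ratio estimate are unaffected, and the two components of the shortfall should be reported separately. But a pilot label can justify choosing 0.1 or accepting lower power; it cannot justify sizing at one level and testing at another. Section 5.2.3 sets 0.05 explicitly and without restriction. A separate analysis plan could not settle the matter without contradicting one of the two sections.

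**Conclusion.** The point holds. Sections 5.1 and 5.2.3 fix different two-sided levels, 0.1 and 0.05, for the same primary comparison. On the inputs as stated, power for the planned test at 0.05 is about 65% (62% to 66% across standard methods), so the chance of missing a hazard ratio of 0.60 is about 35%. If 80% at 0.1 is accepted unverified, the figure at 0.05 is still only 70%. As a secondary point, 80% at 0.1 does not follow from the stated inputs, which give about 76%.

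These figures assume proportional hazards, 1:1 allocation and a full 24 months of follow-up. The simulation and the 84.6-event figure also assume exponential event and withdrawal times. The contradiction between the two levels rests on no assumption.

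**What to change.** Use one significance level in sections 5.1 and 5.2.3, and fix it before the blind is broken. Either option is defensible for an exploratory trial:

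- **Keep 0.05 with the 95% interval**, and restate section 5.1 as about 65% power for a hazard ratio of 0.60, or 80% power for a hazard ratio of about 0.54.
- **Declare 0.10 with a 90% interval**, and restate the power as about 76% on the stated inputs.

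In both cases give the expected number of events (about 82 to 87) and name the method. If the 80% came from another reading of the inputs, state that reading.

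The cost is a sentence in each section and no extra patients. The price is a less flattering power figure or an openly more lenient level.
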